1290 The per-protocol analysis will be performed including only participants who complete all • 1291 required injections without receiving any non-protocol treatments and have data at the 1292 24-week visit. 1293 • The intent-to-treat analysis is considered the primary analysis. If the intent-to-treat and 1294 per-protocol analyses yield the same results, the per-protocol analysis will be used to provide supportive evidence of the magnitude of treatment effect among patients who 1295 received the treatment. If the results of the two methods differ, exploratory analyses will 1296 1297 be performed to evaluate the factors that have contributed to the differences. A sensitivity analysis will be conducted to compare the results from multiple imputation with those 1298 1299 using a per-protocol analysis only including study participants who completed the 24-1300 week visit and with results from last-observation-carried-forward. 1301 1302 Generalized estimating equations (GEE) will be used to adjust for the correlation between eyes 1303 of patients who have two study eyes. 1304 1305 Although expected to be under-powered, pre-planned subgroup analyses will be conducted in the same way as the primary analysis and include stratification by improvement in OCT CSF thickness 1306 during run-in phase visits by $\geq 10\%$ at any visit, and improvement in VA during run-in phase by 5 1307 or more letters at any visit. Other subgroup analyses will be described in the detailed Statistical 1308 1309 Analysis Plan. These subgroup analyses will be used to guide choice of pre-planned subgroup 1310 analyses in the phase III trial. 1311 1312 Imbalances between groups in important covariates are not expected to be of sufficient magnitude 1313 to produce confounding; however, a second analysis that adjusts for imbalanced baseline covariates will be performed. If results are similar to the primary analysis, the primary analysis 1314 will be accepted as the definitive analysis; otherwise, the reasons for the difference will be 1315 1316 explored. 1317 1318 There are no data to suggest that the treatment effect will vary by sex or race and ethnicity. 1319 However, both of these factors will be evaluated in exploratory analyses. 1320 1321 7.4 Secondary Outcomes 1322 In addition to the primary outcome, the following secondary outcomes will be estimated, and their 1323 95% CI will be obtained in each treatment group and compared between treatment groups: 1324 1325 • Percent of eyes with at least 10 and at least 15 letter gain (increase) or loss (decrease) in E-ETDRS letter score visual acuity at 24 weeks 1326 1327 • Visual acuity AUC between randomization and 24 weeks • Mean change in OCT CSF thickness, adjusted for thickness at time or randomization, 1328 1329 using ITT, and per-protocol analyses • Percent of eyes with ≥ 1 and ≥ 2 logOCT step gain or loss in CSF thickness at 24-week 1330 1331 visit • Percent of eyes with OCT CSF thickness (in micros) < the following gender and OCT 1332 machine-specific values at 24-week visit: <290 in women and <305 in men in Zeiss 1333 1334 Cirrus; <305 in women and <320 in men in Heidelberg Spectralis • OCT CSF thickness area under the curve (AUC) between randomization and 24 weeks 1335 • Percent of eyes with worsening or improvement of diabetic retinopathy on clinical exam 1336 1337

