
1338

1339 7.4.1 Secondary Outcomes Analysis

1340 Analyses of secondary outcomes will be conducted as follows:

1341 Binary outcomes will be analyzed using logistic regression to control for baseline level of the

1342 outcome. Continuous outcome comparisons will be performed using ANCOVA with adjustment

1343 for baseline values. All linear model assumptions will be verified including linearity, normality

- 1344 of residuals, and homoscedasticity. If model assumptions are not met, a nonparametric analogue
- 1345 for ANCOVA will be considered. Multple imputation method will be implemented for missing 1346 data. GEE will be used to adjust for correlation between eyes of participants with two study
- 1347 eyes.
- 1348
- 1349

1350 7.5 Safety Analysis Plan

1351 Adverse events will be categorized as study eye, non-study eye, and systemic. The events will be tabulated and compared between treatment groups. Separate analyses will compare related adverse 1352

- 1353 events between groups.
- 1354
- 1355 Specific adverse events of interest will include:
- 1356 Injected-related: increased intraocular pressure, endophthalmitis, retinal detachment, retinal tears, intraocular hemorrhage 1357
- Ocular drug-related: increased intraocular pressure, need for ocular anti-hypertensives, 1358
- 1359 glaucoma surgery or other IOP-lowering procedures, development or worsening of cataract 1360 and cataract extraction, intraocular hemorrhage, inflammation, migration of Ozurdex to the anterior chamber and subsequent corneal complications 1361

1362 Systemic drug-related: Deaths, participants with at least one hospitialization, participants

with at least one SAE, and cardiovascular events and cerebrovascular events as defined by 1363 Antiplatelet Trialists' Collaboration 1364

1365 1366 • Systemic adverse events for participants with two study eves will be evaluated separately from participants with one study eye.

- 1367
- 1368

1369 Further definitions of the events for analysis and the analytic approach will be provided in the 1370 detailed statistical analysis plan.

1371 1372

1373 7.6 Additional Analysis Objectives Related to Design of Phase III Trial

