 - Footnote No. of missing values and No. of values truncated at 3 standard deviation from the mean (if any)¹
 - Review lens status for eyes improved or worsened on visual acuity at 24 weeks [Discussion text]
 - iii. Area under the curve (AUC) between randomization and 24 weeks using truncated data [Figure 2]
 - Mean \pm SD
 - Median [IQR]
 - Note: AUC is computed only for those completing the 24 week follow-up visit.
 - b. Compare change in visual acuity at 24 weeks from randomization between treatment groups
 - Perform Markov Chain Monte Carlo multiple imputation² on missing data (100 imputations) for change in visual acuity at 24 weeks using all available visual acuity data at post randomization follow-up visits, accounting for treatment group assignment, randomization visual acuity value, laterality and improvement in visual acuity during run-in phase. Create flags for binary outcomes specified above based on imputed data.

- ii. Primary analysis: Perform a linear mixed effects model for treatment group comparison of mean change in visual acuity at 24 weeks from randomization. (%*MIAnalyzeMeanMixed* macro)
 - Truncated change in visual acuity letter scores at 24 weeks will be fitted as the dependent variable, and the treatment group as the independent variable, adjusting for randomization visual acuity value, randomization stratification factors (laterality and improvement in visual acuity during run-in phase as defined in the protocol) by including each as a fixed effect in the model. A random subject effect will be included to adjust for the correlation between eyes of participants who have two randomized eyes (assuming a compound symmetry covariance structure).
 - Run the model on observed data to check model assumptions including residual analysis, goodness of fit and influence diagnostics [**not in text**]
 - Run the model on the imputed datasets and report the adjusted mean difference, 95% confidence interval, and *P*-value from treatment group comparison [**Table 2**]
 - Assessment of confounding: Impute the outcome accounting for additional pre-specified potential confounding factors, including age, duration of diabetes, HbA1c levels, retinal thickening on OCT, and diabetic retinopathy severity on clinical exam. All categorical covariates with more than 2 levels are collapsed to a binary covariate for modeling to aid convergence. Mimic primary analysis and obtain *P*-value for treatment group comparison.

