 - Mean \pm SD
 - Median [IQR]
 - Note: AUC is computed only for those completing the 24 week follow-up visit.
- b. Compare change in central subfield thickness (CST) at 24 weeks from randomization between treatment groups
 - i. Perform Markov Chain Monte Carlo multiple imputation² on missing data (100 imputations) for change in CST at 24 weeks using all available OCT CST data at post randomization follow-up visits, accounting for treatment group assignment, randomization visual acuity value, laterality and improvement in OCT CST during run-in phase. Create flags for binary outcomes specified above based on imputed data.
 - ii. Primary analysis: Perform a linear mixed effects model for treatment group comparison of mean change in CST at 24 weeks from randomization (%*MIAnalyzeMeanMixed* macro).
 - Truncated changes in CST at 24 weeks will be fitted as the dependent variable, and the treatment group as the independent variable, adjusting for randomization OCT CST, randomization stratification factors (laterality and improvement in OCT CST during run-in phase as defined in the protocol) by including each as a fixed effect in the model. A random subject effect will be included to adjust for the correlation between eyes of participants who have two randomized eyes (assuming a compound symmetry covariance structure).
 - Run the model on observed data to check model assumptions including residual analysis, goodness of fit and influence diagnostics [**not in text**]
 - Run the model on the imputed datasets and report the adjusted mean difference, 95% confidence interval, and *P*-value from treatment group comparison [**Table 2**]
 - Assessment of confounding: Impute the outcome accounting for additional pre-specified potential confounding factors, including age, duration of diabetes, HbA1c levels, and diabetic retinopathy severity on clinical exam. All categorical covariates with more than 2 levels are collapsed to a binary covariate for modeling to aid convergence. Mimic primary analysis and obtain *P*-value for treatment group comparison. [**not in the text**]
 - Per-protocol analysis [eTable 2]
 - As specified in the statistical analysis plan, the per-protocol analysis will mimic the primary analysis limiting the cohort to 24-week completers who had available data and received

all required injections at the completed visits without receiving any non-protocol treatment. No imputation will be performed.

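### The imputation model for 24-week change in CST lists randomization visual acuity but not randomization CST, although the analysis of those imputations adjusts for randomization CST

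*SAP*

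**What the plan says.** SAP item 5.b.i imputes 24-week change in CST "using all available OCT CST data at post randomization follow-up visits", and "accounting for treatment group assignment, randomization visual acuity value, laterality and improvement in OCT CST during run-in phase". The CST data named are all post-randomization, so randomization CST does not enter by that route either. The logOCT-step indicators are built from the same imputations.

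SAP item 5.b.ii then analyses the imputed datasets with a mixed model, "adjusting for randomization OCT CST, randomization stratification factors" (laterality and run-in improvement in CST).

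The acuity counterpart, item 4.b.i, reads "accounting for treatment group assignment, randomization visual acuity value, laterality and improvement in visual acuity during run-in phase". There the baseline value is the baseline of the outcome being imputed.

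Protocol section 7.4 defines the secondary outcome as "Mean change in OCT CSF thickness, adjusted for thickness at time or randomization". Section 7.4.1 calls for ANCOVA with baseline adjustment for continuous outcomes and for multiple imputation of missing data. It does not say which variables the imputation model should contain.

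**The concern.** An imputation model should contain at least the variables used in the analysis of the imputed data. Here the analysis conditions on randomization CST and the imputation, as written, does not. Imputed changes then fail to follow the relation between change and baseline that the analysis goes on to estimate. That adds noise, distorts the baseline slope and, if missingness depends on baseline CST differently by arm, can shift the treatment difference.

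The results at stake are the intent-to-treat comparison of change in CST, its confounding and sensitivity runs, and the logOCT-step outcomes. The acuity primary outcome is not affected. Nor are the CST AUC, per-protocol, subgroup and machine-specific threshold analyses, which use observed data only.

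**Working it through.** **1. The two models side by side.**

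| Term | Imputation (5.b.i) | Analysis (5.b.ii) |
|---|---|---|
| Treatment | yes | yes |
| Laterality | yes | yes |
| Run-in improvement in CST | yes | yes |
| Randomization acuity | yes | no |
| Randomization CST (CST0) | **no** | **yes** |
| CST at post-randomization visits | yes | 24-week change is the outcome |

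Acuity as an extra imputation variable does no harm. The absence of CST0 is the defect.

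**2. Slip or choice?** Compared with item 4.b.i, the run-in term in 5.b.i was switched to OCT and the baseline term was left as acuity. The confounder list for acuity is "including age, duration of diabetes, HbA1c levels, retinal thickening on OCT, and diabetic retinopathy severity on clinical exam"; that for CST is "including age, duration of diabetes, HbA1c levels, and diabetic retinopathy severity on clinical exam". Retinal thickening was dropped from the second list, which makes sense if baseline CST was thought to be in the model already. Item 5.b.iii ranks randomization CST as the most important of its three covariates. Nothing explains the omission.

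**3. Inputs for the size.** The plan gives no figure for CST, so there is none to reproduce. It does give the expected loss (Protocol 7.2): 70 eyes per group raised to 75 for about 5%. Arithmetic: 70 / 0.95 = 73.7, and 5 / 75 = 6.7%. Both 5% and 6.7% were therefore used, that is 7.5 to 10 of 150 eyes. All CST inputs below are assumptions.

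**4. Main simulation.** 150 eyes 1:1, six visits, monotone dropout, 100 imputations, 1000 trials per cell. Baseline SD 80, 110 or 140 microns (mean 380 before truncation at 305); slope of change on baseline -0.25, -0.40 or -0.55; effect -60 microns; eye-level SD 45; visit-level SD 35; acuity-CST0 correlation -0.3. Analysis: ANCOVA on treatment, CST0 and stratum, with Rubin's rules. Item 5.b.i does not say how follow-up CST enters, so three readings without CST0 were run:

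- A: all visits enter as change.
- B: raw 24-week CST is imputed and CST0 then subtracted.
- C: 24-week change is imputed from raw earlier visits.

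Missing completely at random, 5.0% missing (ranges over the nine cells):

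| Method | Mean SE (microns) | Ratio to 9.51 |
|---|---|---|
| CST0 included | 9.51 | reference |
| Observed eyes only | 9.59 | 9.59/9.51 = +0.8% |
| A | 9.53 to 9.65 | +0.2% to +1.5% |
| B | 9.55 to 9.74 | +0.4% to +2.4% |
| C | 9.68 to 10.21 | +1.8% to +7.4% |

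Under reading C the SE exceeds that from simply dropping the missing eyes. At 6.6% missing (9.57 with CST0) the rises are 0.2% to 1.9%, 0.6% to 3.2% and 2.3% to 9.6%. The actual spread of the estimates rises less: at most 0.6%, 1.7% and 2.7%. Bias is at most 0.19 micron (Monte Carlo error up to 0.11). The baseline slope is flatter by 2% (A), steeper by 1% to 5% (B), or flatter by 6% to 11% (C).

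Dropout tied to CST0 equally in both arms: bias within 0.15 micron for every reading.

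Dropout tied to CST0 in the control arm only:

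| Reading | 4.9% missing | 6.5% missing |
|---|---|---|
| A | -0.3 to -1.1 | -0.4 to -1.3 |
| B | +0.6 to +1.3 | +0.8 to +1.6 |
| C | -1.8 to -3.8 | -2.4 to -4.9 |

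These shifts are in microns, at most 0.46 SE. With CST0 included the shift at 6.5% missing is within 0.1.

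Differences between arms in logOCT-step outcomes (step assumed 0.1 log10 unit) move by at most 0.5 percentage points under random dropout. Under control-arm-only dropout they move by at most 0.6 (A), 1.0 (B) or 1.9 (C).

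**5. Second simulation, other inputs.** Baseline SD 110, SD of change 100, effect -60, correlation of change with baseline -0.3, -0.5 or -0.7; 10 imputations, 300 runs per scenario. With raw follow-up values and 5% missing at random, the SE goes from 15.99 to 16.31 (+2%), 14.56 to 15.14 (+4%) and 12.06 to 13.10 (+9%); bias is within 0.4 micron. On the change scale (correlation -0.5, dropout depending on CST0) it goes from 14.57 to 14.68 (+0.8%). If dropout depends on CST0 in opposite directions in the two arms (correlation -0.5), the estimate moves toward zero by 4.8 microns (raw) or 1.1 (change) at 5% missing, and by 18.7 or 4.5 at 20%.

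**The case against.** The mismatch in the text cannot be disputed, so the other side is about weight.

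- **No breach of the protocol.** Sections 7.4 and 7.4.1 require baseline adjustment in the analysis, which item 5.b.ii provides. They do not prescribe imputation covariates. This stands: the inconsistency lies within the SAP.
- **Some evidence of a slip is indirect.** The ranking in 5.b.iii governs which covariates to drop from non-converging binomial models, and the shorter confounder list may only reflect the adjustment in 5.b.ii. This is fair; the half-edited parallel sentence is the stronger evidence.
- **Arm-specific dropout is implausible.** Protocol 1.3 expects 20% of 125 participants to have two study eyes: 25 participants, so 50 of 150 eyes, one in each arm. If such a participant withdraws, both arms lose an eye. The simulations treated eyes as independent and so probably overstate the shift. Against that, Protocol 1.4 masks participants but not investigators, so arm-related dropout cannot be ruled out.
- **The figures are not bounds.** Every CST input is assumed, and the second simulation exceeds the first one's maximum at 5% missing. This also stands.
- **Raw value or change need not be a separate complaint.** Once CST0 is in a multivariate normal imputation, the two are linear re-expressions of each other, apart from truncation. This is accepted.
- **The program may be right.** The macro code and the separate protocol SAP cited in the SAP Overview were not available. This limits the finding to the text.

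None of these points explains or repairs the omission.

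**Conclusion.** Wrong as written, and minor. The mismatch between items 5.b.i and 5.b.ii is certain; that it is a slip is a well-supported inference; whether the program contains it is unknown.

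If the program followed the text, the cost at the planned loss is a somewhat larger standard error for a secondary outcome, with no clear bias in the treatment effect under random dropout. Shifts of a few microns require dropout that depends on baseline CST differently by arm, for which the documents give no reason. The judgement that the effect is small rests on missingness near the planned 5% to 6.7%; it would not be safe at, say, 20% missing with that kind of dropout. No sample size, power or alpha figure changes.

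**What to change.** In SAP item 5.b.i, add randomization OCT CST to the imputation model. Randomization acuity may stay as an auxiliary variable. With CST0 included, no ruling on raw values versus change is needed, though a sentence recording which was used would help anyone reproducing the analysis.

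Then check the imputation call. If it already contains randomization CST, only the text changes. If not, rerun the CST imputations, the comparison of change in CST with its confounding and sensitivity runs, and the logOCT-step outcomes.

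The cost is one phrase and a program check, plus a rerun only if needed. No new data are required.

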- pathways.³³⁻³⁵ Therefore, rationale exists to assess whether intravitreal steroid treatment 228
- 229 combined with anti-VEGF therapy is more efficacious in reducing center-involved DME than
- 230 anti-VEGF therapy alone.
- 231
- 232 Multiple studies, including two phase III randomized controlled trials conducted by the
- 233 DRCR.net have demonstrated that there is a short-term early increase in visual acuity with
- 234 intravitreal steroid treatment for DME. Although the DRCR.net Protocol B study ("A
- 235 Randomized Trial Comparing Intravitreal Triamcinolone Acetonide and Laser Photocoagulation
- 236 for Diabetic Macular Edema") found that monotherapy with intravitreal steroid is not as
- efficacious as monotherapy with laser treatment alone,¹⁰ there are data to suggest that adjunctive 237
- 238 therapy with intravitreal steroid may have a role in selected eyes with DME. In Protocol I, eyes
- 239 that were pseudophakic at baseline that were treated with intravitreal triamcinolone and laser
- 240 appeared to have similar visual acuity and OCT results as the anti-VEGF-treated eyes.¹² Since 241
- this study is a phase II trial, it will assess a proof of concept for beneficial effect of the 242 combination corticosteroid+anti-VEGF agents. Although this study will include both phakic and
- 243 pseudophakic eyes, the short-term primary outcome at 6 months is not expected to be affected by
- 244 the potential cataract development that is associated with corticosteroid use. Should this study
- 245 show beneficial effect of the combination corticosteroid+anti-VEGF agents in eyes with
- 246 persistent DME short-term, a future longer term phase III trial may be designed to further assess
- 247 the efficacy and safety of this regimen long-term.
- 248

249 Since eligible eyes for this study can be pseudophakic, there is a potential for their macular

- 250 edema to have an inflammatory component from prior cataract surgery in addition to the DME.
- 251 Therefore, eligibility criteria will require that if cataract surgery has been performed, it must
- 252 have been performed at least 9 months before randomization (6 months before enrollment), to
- 253 reduce the chance of a post-cataract surgery macular edema (Irvine-Gass Syndrome) being
- 254 present at baseline.
- 255

256 1.1.6 Combination Steroid and Anti-VEGF treatment for DME

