1147 The 0.7 mg dexamethasone implant (Ozurdex) generally appeared to be safe and well-tolerated in phase III studies in which it was evaluated as treatment for macular edema secondary to retinal 1148 1149 vein occlusion.⁴² No cases of endophthalmitis occurred in these studies which included 1,256 1150 study participants followed for 12 months after enrollment. The 12-month incidence of 1151 subconjunctival hemorrhage ranged from 22.3%-24.9% in study eyes, some of which received 1 1152 and some of which received 2 implants at either the 0.7 mg or 0.35 mg dose. Cataract 1153 progression occurred in 29.8% of phakic eyes that received two 0.7 mg implants versus only 1154 5.7% of sham-treated phakic eves. An increase in IOP of 10 mmHg or more was observed in 1155 eyes that received two 0.7 mg implants at rates of 12.6% after the first implant and 15.4% after the second treatment. A total of 32.8% of study eyes receiving two 0.7 mg implants had at least a 1156 1157 10 mmHg increase in IOP from baseline during the 12 months of follow-up. Of eyes that 1158 received a 0.7 mg implant at baseline, 25.5% were started on an IOP-lowering medication during the first 180 days of the study. When a single 0.7 mg dexamethasone implant was administered 1159 in 55 vitrectomized eyes with DME,⁴⁴ the most common adverse events were conjunctival 1160 1161 hemorrhage (52.7%), conjunctival hyperemia (20.0%), eye pain (16.4%), increased IOP (16.4%), conjunctival edema (12.7%), and vitreous hemorrhage (10.9%). Of the 48 study participants 1162 1163 who were not on IOP-lowering medication at baseline, 8 (17%) began on IOP-lowering medication during the study. Additional adverse events that occurred in more than 5% but less 1164 than 10% of eyes were maculopathy (either epiretinal membrane or macular thickening), anterior 1165 chamber cells, foreign body sensation, iritis, and floaters. Migration of Ozurdex to the anterior 1166 1167 chamber with subsequent corneal edema is a rare complication of Ozurdex injections. This risk is associated with with aphakic eyes, ⁵⁰⁻⁵² and pseudophakic eyes with anterior chamber intraocular 1168 lens and iridectomy or disruption of the posterior capsule.⁵³⁻⁵⁵ In one study of 342 eyes with 1169

- 1170 macular edema due to retinal vein occlusion treated with Ozurdex, two eyes (~0.5%) had
- 1171 Ozurdex dislocated to the anterior chamber requiring surgical repositioning in the vitreous

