Diabetic Retinopathy Clinical Research Network

U1 Manuscript

Continued Ranibizumab With or Without Dexamethasone for Persistent Diabetic Macular Edema (Protocol U):

A DRCR.net Phase 2 Randomized Clinical Trial

Technical Plan

VERSION NUMBER	AUTHOR	APPROVER	EFFECTIVE DATE	REVISION DESCRIPTION
1.0	[name]	[name]	9-25-2017	Initial version

OVERVIEW

Protocol U is a short-term evaluation of combination intravitreous corticosteroid + anti-VEGF treatment for persistent central-involved diabetic macular edema following anti-VEGF therapy.

All potential study participants were required to participate in a 12-week run-in phase. In order to enter the run-in phase, all eligibility criteria were assessed and met. During the run-in phase, study eyes received 3 study ranibizumab 0.3mg injections approximately 4 weeks apart. At the end of the run-in phase, eligible study eyes that still met eligibility criteria were randomly assigned to one of the two treatment groups: A) sham + intravitreal ranibizumab 0.3mg [ranibizumab group], or B) dexamethasone intravitreal implant + intravitreous ranibizumab 0.3mg [combination group]. Study participants may have one or two study eyes. Study participants with two study eyes were randomly assigned to receive continued anti-VEGF therapy (ranibizumab) in one eye and dexamethasone intravitreal implant + ranibizumab in the other eye. Study duration was 24 weeks post randomization.

The protocol statistical analysis plan can be found at this location: \Eros\sys\user\aDRCRN\Protocols\Protocol U - Phase II Persistent DME Study\Statistics\SAP\Protocol U SAP 04-12-17 (8-29-17) ver 2 clean.docx

The purpose of this document is to provide the specific analysis objectives and technical details for the protocol U primary manuscript.

DATA SOURCE

Database used to create SAS data sets: DRCRnet_U_PrimManu_21sep2017

Data validation: \\Eros\sys\user\aDRCRN\Protocols\Protocol U - Phase II Persistent DME Study\Statistics\Data Closeout\Documentation

SAS master data sets

Dataset creation: \\Eros\sys\user\aDRCRN\Protocols\Protocol U - Phase II Persistent DME Study\Master Dataset\Documentation

Location: \\Eros\sys\user\aDRCRN\Protocols\Protocol U - Phase II Persistent DME Study\Master Dataset\Datasets\20170921Frz

SAS master datasets utilized:

- 1. *eyes* one record per eye (study eyes and non-study eyes)
 - a. Read in as *eyesRand*
 - i. Limited to randomized eyes only (randEyeFlg)

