 - Post hoc assessment: impute the data with additional factors including lens status (pseudophakic vs. phakic) and number of anti-VEGF injections (3 vs. more than 3 injections) within 20 weeks prior to run-in. Mimic the prespecified analysis above by including each additional variable one at a time. [Table 2 Footnote]
 - Construct a scatter plot of number of prior anti-VEGF (as a continuous outcome) versus change in visual acuity at 24 weeks by treatment group to explore the potential relationship using observed data. [not in text]
 - Per-protocol analysis [eTable 2]
 - As specified in the statistical analysis plan, the per-protocol analysis will mimic the primary analysis limiting the cohort to 24-week completers who had available data and received all required injections at the completed visits without receiving any non-protocol treatment. No imputation will be performed.

- Report mean ± SD and median [IQR] by treatment group, adjusted mean difference, 95% CI and *P*-value from the treatment group comparison
- Sensitivity analysis [not in text]
 - All sensitivity analyses will mimic the primary analysis model using imputed data.
 - Pre-specified sensitivity analysis will be performed and stratified by sham injection procedure.
 - Post hoc sensitivity analysis will exclude all patients at Site 194.
 - Note: this was at recommendation of DSMC, after review of cases of ineligible participants enrolled at that site discovered at a site visit.
- Subgroup analysis (%*subgrpMixed* macro):
 - Pre-specified subgroup analysis will evaluate the effects of following baseline factors: lens status [eFigure 2], improvement in visual acuity during run-in phase [eFigure 3], and improvement in OCT during run-in phase [eFigure 4]. [eTable 3]
 - Post hoc subgroup analysis will mimic the pre-specified subgroup analysis to examine the effect of the following baseline factors: randomization visual acuity (<64 vs. ≥64 letters), and number of prior anti-VEGF injections within 20 weeks prior to run-in (3 vs. 4 or more injections). [eTable 4]
 - The subgroup analysis will mimic the primary analysis adding an interaction between subgroup and treatment to the primary mixed model using observed data only.
 - Report the *P*-value for the interaction term. Report mean ± SD and median [IQR] by treatment group within each subgroup.

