- Report the observed No. (%) by treatment group, adjusted difference in proportions, 95% confidence interval, and *P*value from treatment group comparisons
- AUC outcome: Mimic the linear mixed effect model in the primary analysis limiting the cohort to 24-week completers. No imputation will be performed.
 - Report mean ± SD and median [IQR] by treatment group, adjusted mean difference, 95% confidence interval, and *P*-value from treatment group comparison.
- 6. Summarize safety events occurred at any time during randomization phase
 - a. Ocular adverse events [eTable 5]
 - i. Tabulate No. (%) of eyes experienced at least one event by treatment group using *eyesRand* dataset
 - At least one ocular adverse events in the study eye
 - Increased intraocular pressure (IOP) events (a composite outcome, defined as any of the below). Each component will also be reported separately.
 - IOP increased \geq 10 mmHg from randomization at any visit
 - \circ IOP \geq 30 mmHg at any visit
 - Received ocular anti-hypertensives
 - Endophthalmitis
 - Inflammation
 - Any retinal detachment (a composite outcome, defined as any of the below). Each component will also be reported separately.
 - Traction retinal detachment
 - Rhegmatogenous retinal detachment
 - Unspecified retinal detachment
 - Retinal tears

- Retinal hemorrhage
- Vitreous hemorrhage
- Cataract extractions
- Glaucoma surgery
- Received post-injection treatment to lower IOP
- Migration of dexamethasone implant to the anterior chamber and subsequent corneal complications (combination group only)
 - Note: There is no specific MedDRA term for this type of adverse event. Instead, perform a manual check by searching for keywords "migration" and "anterior chamber" in the description field on the AE form, limiting to records in randomized eyes at post randomization.
- ii. Compare the frequency between treatment groups using Fisher's exact test and report *P*-value.
- iii. Footnote No. of patients experienced multiple types of ocular adverse events as listed above (if any)
- b. Systemic adverse events
 - i. All systemic adverse events will be reported by treatment group: combination group (unilateral participants), ranibizumab group (unilateral participants), and bilateral participants.
 - ii. Reduce *eyesRand* dataset to patient-level as a temporary dataset *ptRand*
 - iii. Tabulate No. (%) of participants experienced at least one event [eTable 6]
 - At least one systemic adverse event

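### Cataract extraction is tabulated as a percent of all randomized eyes, including pseudophakic eyes that are not at risk, so the reported rate and absolute difference are diluted (minor)

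*SAP*

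**What the plan says.** **Denominator.** SAP item 6.a.i (ocular adverse events, eTable 5) instructs: "Tabulate No. (%) of eyes experienced at least one event by treatment group using" the eyesRand dataset. The Data Source section describes eyesRand as "Limited to randomized eyes only (randEyeFlg)". No lens-status condition is attached.

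**The row.** "Cataract extractions" stands in the list without a qualifier. The same list does state a restriction elsewhere: the implant-migration row is marked "combination group only".

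**The test.** Item 6.a.ii: "Compare the frequency between treatment groups using Fisher's exact test and report" the P-value.

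**Who is enrolled.** Protocol 1.1.5: "Although this study will include both phakic and" pseudophakic eyes. Protocol 2.2.2 excludes aphakia, so a randomized eye is either phakic or pseudophakic.

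**Lens status as a variable.** The lens is assessed at the randomization visit (Protocol 4.3). SAP item 4.b.ii uses "lens status (pseudophakic vs. phakic)" as a post hoc adjustment factor and lens status as a pre-specified efficacy subgroup. It is not used in the safety table. It is not one of the two stratification factors in Protocol 4.4, which are run-in improvement in retinal thickness and in visual acuity.

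**Status of the outcome.** Protocol 1.3 (I) and 7.5 name cataract extraction among the drug-related ocular safety outcomes. The protocol's own risk text (6.5.1.2) gives cataract rates per phakic eye: "progression occurred in 29.8% of phakic eyes that received two 0.7 mg implants versus only" 5.7% of phakic eyes given sham.

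**The concern.** A risk should be expressed over the units that can have the event. Every pseudophakic eye in the denominator lowers the extraction percent in its arm, and lowers the absolute difference between arms. The resulting figure depends on the lens mix of this sample, so it does not carry over to a population with a different mix.

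Randomization does not balance lens status by design. If one arm happens to hold more phakic eyes, the all-eye percents differ for that reason alone. What is at stake is the accuracy of a reported rate for a named steroid-related safety outcome in a trial that lists safety assessment among its objectives (Protocol 1.2).

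**Working it through.** The plan states no expected extraction rate and no phakic share, so there is no planned figure for this row to reproduce. The only plan figure used is the number of eyes: 125 participants with 20% bilateral give 125 x 1.20 = 150 eyes, or 75 per arm, as Protocol 7.1 states.

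**1. Dilution.** Let f be the phakic share.

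all-eye rate = phakic rate x f, and all-eye risk difference = phakic risk difference x f when f is equal in the two arms.

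For f = 0.5 to 0.7 (assumption) the table shows 0.5 to 0.7 of the at-risk values. The risk ratio is unchanged because f cancels.

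**2. Same events, two denominators.** Take f = 0.60, so 75 x 0.60 = 45 phakic eyes per arm. The event counts are illustrative.

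| Events | Of 75 randomized eyes | Of 45 phakic eyes | Fisher P, 75 | Fisher P, 45 |
|---|---|---|---|---|
| 6 v 1 | 8.0% v 1.3% (6.7 points) | 13.3% v 2.2% (11.1 points) | 0.116 | 0.110 |
| 6 v 0 | 8.0% v 0% (8.0 points) | 13.3% v 0% (13.3 points) | 0.028 | 0.026 |
| 2 v 0 | 2.7% v 0% (2.7 points) | 4.4% v 0% (4.4 points) | 0.497 | 0.494 |

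The absolute figures change by a factor of 1/0.60 = 1.67. The P-values do not move in any way that matters.

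**3. Chance imbalance in lens status.** With f = 0.60 and all eyes treated as independent, the SD of the between-arm difference in phakic share is sqrt(2 x 0.60 x 0.40 / 75) = 0.080, or 8 points.

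Bilateral participants contribute one eye to each arm: 20% of 125 is 25 participants, so 25 of the 75 eyes per arm are paired. If fellow eyes always shared lens status (an upper-bound assumption), only the other 50 eyes per arm could create imbalance: sqrt(2 x 50 x 0.60 x 0.40) / 75 = 0.065, or 6.5 points. The SD therefore lies at about 6.5 to 8 points.

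**4. Effect of that imbalance.** Suppose phakic eyes have the same extraction risk in both arms. The all-eye rate ratio is then simply the ratio of phakic shares:

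- 64% v 56% phakic (8 points, one SD if eyes are independent): 64/56 = 1.14.
- 68% v 52% phakic (16 points, two SD): 68/52 = 1.31. With an assumed phakic risk of 10% this reads as 6.8% v 5.2%, a spurious 1.6 points.

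The row restricted to phakic eyes shows no such difference in expectation.

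**The case against.** A reader might infer that the table hides a main steroid harm, or that the safety comparison is biased. The documents do not support that, for these reasons:

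- **Counts are shown.** The number of extractions is reported beside the percent. Only the percent is diluted. Lens status is also a pre-specified subgroup (eTable 3), so approximate phakic numbers may be recoverable.
- **Events should be few.** Post-randomization follow-up is 24 weeks. Protocol 2.2.2 (criterion p) excludes eyes expected to need extraction during follow-up, and 4.2 (criterion h) applies that again at randomization.
- **The test is essentially unaffected.** With balanced arms the planned Fisher's P changes in the third decimal place in the examples above.
- **Large imbalance is unlikely.** A phakic share of 45% v 65%, which would distort the row badly, is a 20-point gap: 20/8 = 2.5 SD, or 20/6.5 = about 3 SD with paired eyes. Chance imbalance is not a systematic bias of the randomized comparison.
- **The cited phakic rates are not a benchmark.** The 29.8% and 5.7% are cataract progression over 12 months in retinal vein occlusion. Extraction at 24 weeks in diabetic macular edema would not be comparable with them on any denominator. They show only that the protocol itself counts cataract risk in phakic eyes.
- **Phase III planning does not hinge on this row.** Protocol 7.6 does not list a cataract extraction rate among its design inputs.

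All of these points stand, and they limit the size of the issue.

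One further objection is weaker. The document reviewed is a technical plan for the primary manuscript. It refers to a separate statistical analysis plan, and part of its own text was not available. A phakic denominator could be written there. But item 6.a.i itself names the dataset, and the same list states a restriction for another row where one is meant, so as written the rule is all randomized eyes.

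**Conclusion.** The point holds, at minor severity. As written, the cataract extraction row divides by eyes that cannot have the event. The percent and the absolute difference are reduced to the phakic share of their at-risk values: 0.5 to 0.7 if 50-70% of eyes are phakic, which is an assumption. They can shift modestly more with chance lens-status imbalance (SD about 6.5 to 8 points at 60% phakic and 75 eyes per arm).

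It would go too far to say that a steroid harm is concealed or that the safety conclusion would change. With lens status balanced the risk ratio is the same, Fisher's P is nearly the same, and few events are expected. What is gained is a correct at-risk rate.

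**What to change.** In SAP item 6.a.i, specify that cataract extraction is reported as n/N (%) among eyes phakic at randomization, show the phakic N for each arm, and apply the Fisher's exact test of item 6.a.ii to that denominator. A risk difference with 95% CI would be a useful addition but is optional, since no other row in the table is planned with one.

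The cost is one line of wording and a filter on a variable already collected. No new data are needed, and the primary analysis and trial conduct are untouched.
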